8.3.3.3. Expectedness

The Medical Monitor will be responsible for determining whether an AE is expected or unexpected. An AE will be considered unexpected if the nature, severity, or frequency of the event is not consistent with the information described in the Investigator's Brochure.

Refer to the Investigator's Brochure for the expected/anticipated events.

8.3.4. Reporting of AEs

Report initiation for all AEs and SAEs will begin at the time of the first treatment visit and continue until the end of final study visit. All events will be followed to resolution or until the patient completes the study. A final assessment of outcome will be made at that time.

All AEs must be recorded in the patient's study records. AEs will be reported using customary medical terminology along with the following information: the onset and end dates, whether the event is considered to be a SAE (see Section 8.3.2), the impact the event had on study treatment (see Section 8.3.4.1), the grade (intensity) of the event (see Section 8.3.3.1), the causality of the event (see Section 8.3.3.2), whether treatment was given as a result of the event (see Section 8.3.4.2), and the outcome of the event. (see Section 8.3.4.3).

8.3.4.1. Impact on Study Treatment

The impact the event had on the study treatment will be assessed as either: dose increased, dose not changed, dose rate reduced, dose reduced, drug interrupted, drug withdrawn, not applicable, or unknown. The "not applicable" assessment will be used only when the patient is no longer in the Treatment Phase of the protocol.

8.3.4.2. Treatment Given as a Result of the Event

[figure not shown]
The event impact in terms of treatment provided will be as either: none, medication administered, non-drug therapy administered, hospitalization, or other (with a specification).

8.3.4.3. Outcome Assessment

The outcome of the event will be assessed as either: fatal, not recovered/not resolved, recovered/resolved, recovered/resolved with sequelae, recovering/resolving, or unknown. Only one AE per patient is allowed to have an outcome assessment as "death." If there are multiple causes of death for a given patient, only the primary cause of death will have an outcome of death.

8.3.5. Reporting of SAEs

The Investigator is required to report all SAEs that occur during the time period specified in Section 8.3.4. Once the Investigator becomes aware of an SAE, he/she must report the SAE to Medical Monitor within 24 hours.

The Medical Monitor may request additional supporting documentation as it becomes available, such as lab reports, electrocardiogram [ECG] reports, discharge summary, hospital notes, etc., if applicable. Additional follow-up information as it becomes available must be reported to the Medical Monitor.

The Investigator is also responsible for reporting all SAEs to the appropriate Institutional Review Board (IRB) in accordance with local laws and regulations. The Investigator is responsible for maintaining documentation in the study file that indicates the IRB has been properly notified.

8.3.6. SAE Follow-Up

All patients experiencing an SAE, including the discontinued patients, must be closely followed until sufficient information is obtained to indicate a return to normal status or until the event stabilizes at a level acceptable to the investigator (i.e., recovery, return to baseline status, no further improvement expected, or death).

For each SAE indicated as an unresolved event on the initial report, regardless of whether the patients completed the study or withdrew, the site should submit a follow-up report with updated information.

9. STATISTICAL ANALYSIS

This section presents general information about statistical considerations and concepts and a brief discussion on analysis methodology, as well as some data conventions. Detailed descriptions of the statistical analysis methods and data conventions that will be used in this study will be in a separate document [i.e., the Statistical Analysis Plan (SAP)].

9.1. TREATMENT ARMS

There will be two treatment arms in the study:

- **Arm A:** Best supportive and/or standard of care in combination with CX-4945 1000 mg BID PO or
- **Arm B:** Best supportive/standard of care

9.2. DESCRIPTION OF STUDY OUTCOMES (ENDPOINTS)

For description of study outcomes see the Objectives and Endpoints in Section 1.1 and Section 3.

9.2.1. Safety Measures:

- Incidence and severity of AEs
- Incidence of SAEs
- Incidence of AEs and SAEs leading to discontinuation of study medication.
- Changes in blood chemistry (including electrolyte abnormalities), hematology and coagulation parameter results
- Changes in vital signs including temperature, pulse, respiratory rate, systolic and diastolic blood pressure
- Changes in physical examination results
- Changes in ECG results

9.3. SAMPLE SIZE DETERMINATION AND RATIONALE

A total of approximately 20 subjects will be randomized 1:1 in this study. The sample size is based on clinical judgment. No statistical power calculation is used to establish the sample size for this proof-of-concept study.

9.4. RANDOMIZATION

The randomization will use block size of 2 or 4 with a 1:1 ratio of CX-4945 in addition to SOC group and SOC alone group to ensure balanced distribution of subjects. An individual, independent

of the clinical trial team, will develop the randomization schedules. Subjects who have provided written informed consent and have met all the inclusion criteria and none of the exclusion criteria will be randomized to one of the treatment groups.

9.5. BLINDING

This is an open label study.

9.6. INTERIM ANALYSIS

No Interim Analysis (IA) is planned for this study.

9.7. GENERAL STATISTICAL CONSIDERATIONS

All collected study data will be presented in patient data listings. Statistical analyses will be performed using SAS® for Windows, version 9.4 or later. Descriptive statistics (n, mean, standard deviation, median, minimum and maximum) will be presented by treatment group for continuous variables. Frequencies and percentages will be presented by treatment group for categorical variables.

9.7.1. Analysis Populations

9.7.1.1. Intent-to-Treat (ITT)Population

The **ITT population** is defined as all randomized patients. This population will be used as the primary analysis population for analysis of the primary and secondary efficacy endpoints.

9.7.1.2. Per Protocol (PP) Population

The PP population is defined as the set of patients who meet the ITT population requirements and are not associated with any major protocol violations. This population will be identified before the database lock. This population will be used as the supportive analysis population for analysis of the primary and secondary efficacy endpoints.

9.7.1.3. Safety Population

The Safety population is defined as any patient receiving at least one dose of CX-4945 or standard of care treatment after randomization. This population will be used for the analysis of safety parameters.

9.7.1.4. PK Population

The PK population includes all patients receiving at least one dose of CX-4945 and have adequate blood samples provided for PK evaluation and calculation of the PK parameters. PK data collected in two CX-4945 studies will be used for PK analysis.

9.7.2. Covariates

For efficacy analyses important prognostic factors that need adjustment will be specified in the SAP for the study

9.7.3. Missing Data

The method for handling missing data will be included in the statistical analysis plan. Every effort will be made to obtain required data at each scheduled evaluation from all patients who have been randomized in the study to minimize missing data. However, in the event when there are missing data the following imputation methods will be used.

For efficacy evaluations, multiple imputation methods will be used to handle missing data and will be detailed in the SAP. This imputation method is a robust method to impute potential missing measurements. The imputation will be carried out in SAS version 9.4 or later using PROC MI.

9.8. ANALYSIS METHODS

An SAP will be developed and approved before the database is locked. The SAP will present the detailed statistical methodology to be used in analyzing the data from this trial.

9.8.1. Patient Disposition

The disposition of all patients who signed an ICF will be provided. The number of subjects screened, screen failed, received at least one treatment, completed, and discontinued during the study, as well as the reasons for all discontinuations will be summarized by treatment group. Disposition and reason for study discontinuation will also be provided as a by-patient listing.

9.8.2. Demographic and Baseline Characteristics

Demographics and baseline characteristics including medical history, prior and concomitant medications/therapies will be summarized by treatment group using appropriate descriptive statistics.

9.8.3. Concomitant Medications/Therapies

Concomitant medications/therapies will be summarized separately for the Safety population. All prior and concomitant medications recorded in the case report form will be coded to matching Anatomic Therapeutic Classification codes using the most recent version of the WHO Drug Dictionary. Descriptive summaries by treatment group will be prepared using the coded term. All concomitant medications/therapies recorded in the case report form will be listed.

9.8.4. Study Outcome Assessment

For continuous variables data will be summarized by treatment using n, mean, SD, minimum and maximum values. For categorical variables data will be summarized by treatment using frequency and percentage. No inferential statistics are planned. The Safety population will be used for the analysis of safety outcomes.

9.8.4.1. Efficacy Analysis

Analysis of the efficacy endpoints will be summarized according to the variable type and will be detailed in the SAP.

9.8.4.2. Supportive Analysis

To assess the consistency of the primary analysis results, supportive analysis will be conducted using the ITT and PP populations. Statistical methodology for the supportive analyses will be the same as that of the primary analysis, with the exception of the analysis population used.

9.8.4.3. Safety Summaries

Adverse Events

AEs will be coded using the most recent version of Medical Dictionary for Regulatory Activities (MedDRA). Treatment Emergent AE's (TEAE) are defined as events with an onset on or after the first treatment. TEAEs will be summarized by treatment group, system organ class, and preferred term. The following TEAE summaries will be provided:

- Overall (i.e., regardless of severity or relationship to treatment);
- By intensity (mild, moderate, severe, life threatening or death);
- By causality (definitely, probably, possibly, remotely or unrelated);
- By impact on study treatment (dose increased, dose not changed, dose rate reduced, dose reduced, drug interrupted, drug withdrawn, not applicable, or unknown).

In addition, separate summaries of SAEs, and AEs resulting in discontinuation of study treatment will be presented.

Clinical Laboratory Data

All laboratory values will be listed. Laboratory measurements will also be summarized and presented by treatment group and time point.

ECG

All ECG values will be listed. ECG measurements will also be summarized and presented by treatment group and time point.

Vital Signs

All vital sign findings will be listed and/or summarized.

Physical Examination

All physical examination findings will be listed and/or summarized.

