2.4. RISKS/BENEFITS ASSESSMENT

CX-4945 is a generally well-tolerated medication. Most adverse events reported were mild to moderate in severity. The most common toxicities associated with CX-4945 were gastrointestinal disorders, manageable with drug discontinuation or use of anti-diarrheal medication. As CX-4945 is an inhibitor of the host protein kinase CK2, it does not impact the effectiveness of other antiviral drugs or contribute to the emergence of viruses with reduced susceptibility to the drug. Based on the currently available data, the identified or potential risks of the product do not outweigh its identified or potential benefits.

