3. STUDY OBJECTIVES AND ENDPOINTS

Primary Objective	Primary Endpoint
To assess safety and tolerability of CX-4945 administered orally BID to patients with moderate COVID-19	
Adverse events occurring from randomization (Day 1) to Day 60 (including vital signs, physical findings, clinical laboratory, and ECG results) as characterized by type, frequency, severity [(as graded by Toxicity Grading Scale for Healthy Adult and Adolescent Volunteers Enrolled in Preventive Vaccine Clinical Trials (https://www.fda.gov/media/73679/download)], timing, seriousness, and relationship to study therapy.
Secondary Objectives	Secondary Endpoints
To compare time to normalization of COVID-19-related clinical signs in CX-4945 treatment arm versus the control arm.	
Number of days from Randomization (Day1) to the day when the following clinical signs are back to normal as evaluated at every visit during the treatment period (Day 1, Day 4, Day 8, Day 11 and Day 14) and at Follow-up visits on Day 28 and Day 45 :
 
Fever is $\leq 36.6^{\circ}\text{C}$ from axillary site, or $< 37.2^{\circ}\text{C}$ from oral site or $< 37.8^{\circ}\text{C}$ from rectal or tympanic site)Respiratory rate is < 20 bpm while breathing room air at sea level$\text{SPO} \geq 96\%$ in room air without shortness of breath or dyspneaHeart rate < 90 beats per minute 
Note: If some signs listed above were caused by other conditions documented in the medical history and started before COVID-19, the patient can be considered as recovered, when these signs return to the previous (pre-COVID-19) values.

To compare duration of COVID-19-Related clinical symptoms in CX-4945 treatment arm versus the control arm.	Number of days from Randomization (Day1) to the day when: 
No key COVID-19-related symptoms scored higher than 1 as documented using a Patient Reported Outcome (PRO) instrument (a Patient Diary for Assessment of Common COVID-19-Related Symptoms – see Appendix 3),

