6.1.5. CX-4945 Dose Modifications

The most common drug related adverse events reported for CX-4945 are predominantly gastrointestinal disorders, including nausea, vomiting and diarrhea. The dose interruption, reduction, and permanent discontinuation for any toxicity are described below. Dose modification instructions provided below do not substitute for an investigator's medical judgement. Investigators should always manage their patients according to their medical judgement based on the particular clinical circumstances.

**Table 3: CX-4945 Dose Modification and Management for Potential Toxicities
(Attributable to CX-4945)**

Grade* (attributable to CX-4945)	Treatment Modifications
Grade 1	Treat on time, dose reduction is not required
Grade 2	Hold until \leq Grade 1, resume at same dose
Grade 3	Hold until $<$ Grade 2, resume at dose reduced by 1 level (200 mg)
Grade 4	Hold until $<$ Grade 2, resume at dose reduced by 1 level (200 mg). Permanent discontinuation can be considered at the Investigator's discretion

* *Toxicity Grading Scale for Healthy Adult and Adolescent Volunteers Enrolled in Preventive Vaccine Clinical Trials: <https://www.fda.gov/media/73679/download>*

- **Dose Reduction:** If a dose-response relationship for toxicity is observed, then a reduced dose can be given to the patient. Dose adjustments will be allowed based on the toxicity, efficacy evaluation, and clinical judgment by a physician.
- **Dose Interruption:** Refer to **Table 3** above. Recovery to acceptable levels must occur to allow CX-4945 continuation.
- **Dose Discontinuation:** Treatment with CX-4945 can be discontinued prematurely due to the following reasons:
 - Disease progression
 - Respiratory failure requiring invasive mechanical ventilation,
 - Shock (defined by SBP < 90 mm Hg, or Diastolic BP < 60 mm Hg), or
 - Multiple organ dysfunction/failure
 - Intolerable toxicity most probably attributable to CX-4945.
 - Withdrawal from the study treatment or participation
 - Pregnancy
 - Significant study therapy non-compliance
 - If any clinical adverse event, laboratory abnormality, or other medical condition or situation occurs that continued treatment under the protocol would not be in the best interest of the patient.

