8.3.3. Classification of AEs

8.3.3.1. Severity of AE

As study population is outpatients with moderate COVID-19, a standardized toxicity grading scale is modified to reflect the study population. Toxicity Grading Scale for Healthy Adult and Adolescent Volunteers Enrolled in Preventive Vaccine Clinical Trials will be used for grading AEs associated with systemic (general) abnormalities, vital signs, illnesses and lab abnormalities. Full guidelines may be obtained at <https://www.fda.gov/media/73679/download>.

Table 6. Toxicity Grading General Guidelines

Grade	Description
Grade 1	Mild; No interference with activity
Grade 2	Moderate; Some interference with activity not requiring medical intervention
Grade 3	Prevents daily activity and requires medical intervention
Grade 4	Potentially Life-threatening ER visit or hospitalization
Grade 5	Death related to AE.

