**14.3.1.4 Treatment Emergent AE – Subjects with Grade  $\geq 3$  AE**
**14.3.1.5 Treatment Emergent AE – Subjects with Grade  $\geq 3$  Treatment-Related AE**

Population: Safety Population

Characteristics	Treatment Group
(Multi-Selection by Severity Grade, System Organ Class and Preferred Term)	
N	XXX
At least one below [Event#:Subj#]	XXX : XXX (XXX.X%)
~ Repeat Severity Grade:	
Grade $\geq 3$ , Grade 4, Grade 5	XXX : XXX (XXX.X%)
~ <MedDRA Body System1>	XXX : XXX (XXX.X%)
~ <MedDRA Preferred Term 1>	XXX : XXX (XXX.X%)
~ <MedDRA Preferred Term 2>	XXX : XXX (XXX.X%)
~ <MedDRA Preferred Term 3>	XXX : XXX (XXX.X%)
~ <MedDRA Body System2>	XXX : XXX (XXX.X%)
~ <MedDRA Preferred Term 1>	XXX : XXX (XXX.X%)
~ <MedDRA Preferred Term 2>	XXX : XXX (XXX.X%)
~ <MedDRA Preferred Term 3>	XXX : XXX (XXX.X%)

*[For 14.3.1.5] Treatment Related is defined as Definitely Related, Probable Related, or Possibly Related*

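### The SAP adverse-event shells do not separate Grade 1 from Grade 2, so the protocol's summary by intensity is not delivered, and SAP section 1 does not declare the change

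*Protocol*

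**What the plan says.** Protocol section 3 defines the primary endpoint as adverse events from randomization to Day 60, "as characterized by type, frequency, severity" and by further features. Section 9.8.4.3 lists the TEAE summaries to be produced by treatment group, system organ class (SOC) and preferred term (PT). One of them is "By intensity (mild, moderate, severe, life threatening or death", which is five levels.

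Table 6 in Protocol 8.3.3.1 gives the matching grades. Grade 1 is mild and leaves activity undisturbed. Grade 2 is "Moderate; Some interference with activity not requiring medical intervention". Protocol 2.4 says of experience to date: "Most adverse events reported were mild to moderate in severity".

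The introduction to SAP section 1 states that the methods follow Protocol Amendment 1.0 apart from the exceptions set out there. Those exceptions (1.1 to 1.6) cover visit adjustment, the per-protocol population, compliance, inferential and analysis methods, missing data and pharmacokinetics. In SAP 14.3.1.4 and 14.3.1.5, the only shells that give grade by SOC and PT, the severity rows are "Grade $\geq 3$ , Grade 4, Grade 5". The overview table 14.3.1.1 uses the same three rows.

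**The concern.** The protocol promises a five-level description of a primary-endpoint feature. The shells show the upper end of the scale and leave the lower two levels merged inside the all-grade counts. On the protocol's own account, those two levels are where most reported events have fallen. They also differ in meaning: one does not interfere with activity and the other does.

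This is a small, open-label study with no power calculation, so description is its main product. If the tables are programmed as drafted, the report will not show by arm how many patients had moderate rather than mild events. Nothing in the SAP will explain why the promised summary is absent.

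**Working it through.** The documents state no figure on this point, so there is nothing to reproduce. The check has two parts: which grade rows exist, and whether Grade 2 can be derived from them.

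**1. Grade rows in the SAP adverse-event shells**

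| SAP shell | What is counted by arm | Grade rows |
|---|---|---|
| 14.3.1.1 | Any TEAE; treatment-related TEAE; action taken; serious events | ≥3, 4, 5 (for any and for treatment-related) |
| 14.3.1.2, 14.3.1.3 | All TEAEs and treatment-related TEAEs, by SOC and PT | none |
| 14.3.1.4, 14.3.1.5 | Grade ≥3 TEAEs, all and treatment-related, by SOC and PT | ≥3, 4, 5 |
| 14.3.1.6 | Action taken, by SOC and PT | none |
| 14.3.1.7, 14.3.1.8 | Serious events and SUSARs | none |

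Of the five promised levels, mild and moderate have no row of their own in any shell.

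**2. What subtraction can recover**

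For one arm, let A be the number of subjects with any TEAE and H the number with at least one event of Grade 3 or above. Both are in 14.3.1.1. Then

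- subjects whose worst grade is 1 or 2: P = A − H
- subjects whose worst grade is 2: anywhere from 0 to P.

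The same subtraction works within an SOC or PT (14.3.1.2 minus 14.3.1.4, or 14.3.1.3 minus 14.3.1.5) and meets the same limit.

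The counts below are assumed, purely for illustration. About 20 patients randomized 1:1 (Protocol 9.3) gives about 10 per arm.

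| A | H | P = A − H | Worst grade 2 could be |
|---|---|---|---|
| 8 | 1 | 7 | 0 to 7 of 10 |
| 6 | 1 | 5 | 0 to 5 of 10 |
| 4 | 0 | 4 | 0 to 4 of 10 |

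Take the first row for both arms. The planned rows agree: 8/10 versus 8/10 for any event, and 1/10 versus 1/10 at Grade 3 or above (Fisher p = 1.0 for each). The hidden split could still be 7/10 versus 0/10 at worst grade 2. As a yardstick only, the two-sided Fisher p for that split is 2 × C(10,7)/C(20,7) = 2 × 120/77,520 = 0.003. The SAP adverse-event shells have no p-value column, and none is needed. The point is that identical planned output is compatible with any split from none to all of the pooled group.

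**The case against.** Several points on the other side stand and limit the concern.

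- **The SAP does not announce that it removes the summary.** Because it follows the protocol except where it lists a change, the intensity summary formally still applies. This is an unreconciled omission from the shells, not a stated decision.
- **Low-grade events are tabulated.** 14.3.1.1 to 14.3.1.3 count events of every grade by arm. Only the division between Grades 1 and 2 is missing.
- **The information is not lost.** Protocol 8.3.4 requires a grade for every adverse event, and 9.7 promises patient listings of all data. With about 20 patients, Grade 2 could be counted by hand if the listing carries grade; its layout is not in the documents. A listing is still not the by-arm summary that was promised.
- **The counts above are invented.** They show what is possible, not what is likely. Protocol 2.4 describes events already reported and is not a forecast for this trial.

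Two stronger readings are tempting, and the documents support neither.

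First, a reader might infer that dose holds are hidden. In Table 3 of Protocol 6.1.5, Grade 1 reads "Treat on time, dose reduction is not required", while Grade 2 is the lowest grade with a hold, after which patients "resume at same dose". But Table 3 concerns toxicity attributable to CX-4945, so holds arise only in Arm A. They appear as drug interruptions in SAP 14.3.1.1 and, by SOC and PT, in 14.3.1.6. SAP 14.1.9 also shows drug interruption, along with mean daily dose and compliance. What cannot be read between arms is the frequency of Grade 2 events, not the holds.

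Second, a reader might infer that the trial would report no difference in severity. No rule in these shells produces such a conclusion: they contain neither a test nor a difference column.

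**Conclusion.** The point holds in a limited form. The protocol promises five intensity levels for a feature of the primary endpoint. The planned tables give no separate count for two of them, and SAP section 1 does not say so. Grade 2 frequency by arm cannot be read from the planned tables; only Grades 1 and 2 pooled can be obtained. The resulting uncertainty can be as wide as the whole pooled group, for example 0 to 7 of 10 in the first illustration.

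This rests on reading the protocol's five intensity words as Grades 1 to 5 of Table 6, and on the shells being programmed as drafted. It does not rest on the illustrative counts. The change should be made before the tables are produced: the gap is descriptive, but it touches the primary endpoint and is cheap to close.

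**What to change.** 1. In SAP 14.3.1.1, add Grade 1 and Grade 2 rows by arm, for all TEAEs and for treatment-related TEAEs. Count each subject once, at the worst grade. That is a sensible convention, but the protocol does not state it, so the SAP should. The table is headed multi-selection, so the new rows need a label showing that they follow a different counting rule.
2. Extend 14.3.1.4 and 14.3.1.5 to all five grades by SOC and PT, and retitle them. This delivers the summary in Protocol 9.8.4.3.
3. If the sponsor prefers not to do this, list the omission in SAP section 1 and give the reason.

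The cost is a few more table rows. Grade is already recorded for every event, so no new data are needed, and no dose rule changes.
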